1.3.1 Risks from study examinations (PET and magnetic resonance imaging)

In the present study each patient will undergo 3 PET and 2 magnetic resonance imaging (MRI) examinations as well as 2 routine clinical thorax/abdomen computed tomography (CT) examinations.

The radioactivity exposure during a single PET examination (300 MBq) renders radiation exposure of 1.15 mSv (ED of 3.85 µSv/MBq; AstraZeneca dosimetry study on line: SP-PET-0052), which is less than half a year background radiation exposure in Sweden. The thorax CT radiation exposure is 0.8mSv. Total radiation exposure of 3 PET examinations (900 MBq, 3.465 mSv) and 2 CT examinations (1.6 mSv) will not exceed 7 mSv. In addition, permission will be obtained from the Radiation Safety Committee at the PPD [REDACTED], on the appropriateness of this radiation dose.

The total amount of mass injected per single PET examination will not exceed 10 µg (total 30 µg during the study period, which is significantly below the maximum dose (100 µg) allowed for a microdose defined by both the EMA (European Medicines Agency 2009) and the FDA (US Department of Health and Human Services 2006).

Other risks associated with PET examinations include pain and/or haematoma from the arterial and venous punctures. Arterial occlusion may occur. Coagulation testing will be performed during screening, and Allen's test will be performed at screening and prior to the PET examination. The arterial catheter will be inserted at the PET centre under local anaesthesia and, if necessary, emergency care can be provided by PPD [REDACTED]

Risks from MRI scans are associated with the possible presence of magnetic metallic implants, such as pacemakers or hearing aids that may be dislodged during MRI (see Section 3.2). In case of emerging anxiety during the examination the patient will be able to press an emergency button and immediately will be taken out of MR system. Specific study

exclusion criteria will minimize this risk, and strict safety protocols applied daily in clinical care will be in place to prevent risk occurrence. The contrast injection in gadolinium-enhanced MRI sequences carries a low risk of allergic reactions. The MRI staff are specifically trained and there are specific routines to manage unusual complications. Overall, the MRI investigations involve very low risk and the results of the investigations are crucial for the study, both for ensuring inclusion criteria are met, for use in PET data analysis and to follow early efficacy on tumour growth.

Lumbar puncture will be performed on 2 occasions to obtain cerebrospinal fluid (CSF) samples. The procedure-related risks are few. The procedure may cause temporary headache. The risk for local pain and infection are managed by following routine clinical procedures including local anaesthesia and aseptic techniques.

1.4 Study design

This is an open-label, single centre Phase I study to determine the brain exposure of [¹¹C]osimertinib in patients with NSCLC. This study will be conducted in patients with EGFRm NSCLC with BM. The study will consist of 2 phases, an imaging phase and a CAP (Figure 1A). The patient's participation in the imaging phase of the study will be approximately 32 days. The imaging phase of the study will include 3 single intravenous microdose administrations of [¹¹C]osimertinib and positron emission tomography examinations on: Day 1, Day 2 (or up to Day 8) and Day 29 (see Section 5.3.2). Osimertinib 80 mg once a day will be taken by the patient from the day of the second PET examination for at least 21 days before the PET3 examination will be scheduled.

Positron emission tomography examinations using a microdosing approach (Lee and Farde 2006, Saleem et al 2015) will be used, i.e. osimertinib will be labelled with ¹¹C and administered IV at a microdose (<10 µg).

A sufficient number of eligible patients (approximately 12) will be enrolled in order to obtain at least 8 evaluable patients with BM. An evaluable patient is defined as a patient who completes at least 2 PET examinations; 1 with a single IV microdose of [¹¹C]osimertinib alone and another with a co-administered oral 80 mg osimertinib and [¹¹C]osimertinib microdose administration.

The identified study population is considered sufficient to examine variability in pharmacokinetic (PK) and PET examinations. The patients will need to have confirmed EGFRm status by either local or central testing. Epidermal growth factor receptor mutation positive status can be confirmed via assessment of tissue or cytological sample from primary or metastatic tumour. All patients will have a baseline brain MRI for eligibility (presence of BM) and for anatomical and manual delineation of brain regions to be applied in PET image analysis (and for detection of BBB disruption). **CCI**

Brain MRI will include (but is not limited to) T1 (gadolinium enhanced), T2/FLAIR and diffusion-weighted imaging (DWI).

Thorax/abdomen CT will be performed as routine clinical examination and will serve for the diagnosis and evaluation of primary lung tumour and other metastatic sites. It will be repeated at the end of study treatment (on Day 25 ±4 days), to follow potential early effects on tumours.

Positron emission tomography examination of the brain using [¹¹C]osimertinib (administered before the start of PET) will be carried out 3 times: the first time at baseline (PET1; Visit 2 [Day 1]), the second time after the first oral dose of osimertinib of 80 mg (PET2; Visit 3 [Day 2], or within 1 week after baseline) and the third time after 3 weeks treatment with 80 mg oral dose osimertinib daily (PET3; Visit 5 [Day 29]) (Figure 1B).

At each PET examination [¹¹C]osimertinib will be given IV as a microdose (<10 µg), at a radioactivity of 300 MBq/70 kg of body weight. The minimum injected radioactivity will be 200 MBq/70 kg of body weight and the maximum injected radioactivity will be 330 MBq/70 kg of body weight. Brain radioactivity will be measured for 90 minutes (minimum 60 minutes) in the PET examination system (high resolution research tomograph [HRRT]).

The PET2 examination and the PET3 examination will be performed on Visit 3 and Visit 5 after IV [¹¹C]osimertinib administration. The IV dose will be given ~6 hours after the oral osimertinib 80 mg to coincide with the median time of maximum drug concentration (T_{max}) of the oral dose. All participants will receive at least 3 weeks (21 days) treatment with 80 mg oral dose of osimertinib once daily between the PET2 examination and PET3 examination visits.

[figure not shown]
On completion of the imaging phase (ie, at the PET3 examination), patients may continue to take osimertinib tablets (80 mg once daily) as a single agent in the CAP depending on agreement between the patient and the Investigator. This will continue until, in the opinion of the Investigator, the patients are no longer deriving clinical benefit, or the patients stop taking osimertinib for any other reason. No clinical data will be collected during this phase other than sudden death of unknown reason, SAEs that may or may not be related to osimertinib, outcomes of pregnancy and IP dispensing/accountability (Figure 1).

Dose reduction of osimertinib (to 40 mg once daily) according to clinical practise will be allowed in the CAP if deemed necessary by the Investigator due to AEs.

[figure not shown]
Patients not participating in the CAP or who discontinue treatment during the imaging phase will return to the clinic for follow-up assessments 30 days (±7 days) after their last dose of osimertinib in the imaging phase. If the patient's last dose of osimertinib is in the CAP, the patient should be contacted 30 days after their last dose of osimertinib to follow up any existing SAEs and monitor for new SAEs that may be related to the IP, and record any sudden deaths of unknown cause.

Figure 1 **Study flow chart**

A: Study flow

[figure not shown]

B: Study period (drug administration and imaging measurements)

[figure not shown]

C: PET examination flow

PET1 examination

PET2 examination and PET3 examination

● = Tablet dosing

CT: Computed tomography; IV: Intravenous; MRI: Magnetic resonance imaging; PET: Positron emission tomography.

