5. Patients taking rosuvastatin should have creatine phosphokinase levels monitored (due to BCRP-mediated increase in exposure). If the patient experiences any potentially relevant AEs suggestive of muscle toxicity including unexplained muscle pain, tenderness, or weakness, particularly if accompanied by malaise or fever, rosuvastatin must be stopped and any appropriate further management should be taken.
6. Refrain from hard physical training (such as heavy lifting) for a period of 7 days following arterial catheterisation.

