AE: Adverse event; BM: Brain metastases; CSF: Cerebrospinal fluid; CT: Computed tomography; ctDNA: Circulating tumour DNA; ECHO: Echocardiogram DNA: Deoxyribonucleic acid; ECG: Electrocardiogram; EGFR: Epidermal growth factor receptor; FSH: Follicle-stimulating hormone; HBV: Hepatitis B virus, HCV: Hepatitis C virus; HIV: Human immunodeficiency virus; IP: Investigational product; IV: Intravenous; MRI: Magnetic resonance imaging; MUGA: Multigated radionuclide angiogram; LH: Luteinising hormone; PET: Positron emission tomography; PK: Pharmakonitetics; RNA: Ribonucleic acid; SAE: Serious adverse event; WHO: World Health Organisation.

- a Study procedures designated for a specific visit should be performed in 1 day whenever possible and in the best interest of the patient. If this is not possible and/or not in the best interest of the patient, study procedures may be performed across more than 1 day, but within the visit window.
- b Day -1 is the day before dosing. All Day 1 procedures must be performed on Day -1 or pre-administration on Day 1 provided the results are reviewed before dosing. If the patient has been screened within 48 hours of Day 1, safety laboratory tests (haematology, coagulation, biochemistry and urine analysis) do not need to be repeated.
- c PET2 can be conducted on Day 2 (1 day after the PET1 or within the 1 week of PET1 ie, 1 to 6 days of [¹¹C]osimertinib washout is allowed).
- d A clinical visit will be scheduled for when the patient has been on the continuous IP administration for 10 days (window of ± 2 days).
- e The clinical visit for the PET3 examination and CT-2, MRI-2 can be conducted on the same day or on a different day. If the assessments cannot be conducted on the same day, the CT-2, MRI-2 can be conducted within a window of 7 days.
- f Full ophthalmic assessment, including slit lamp examination, will be performed at screening and if a patient experiences any visual symptoms (including blurring of vision), with additional tests, if clinically indicated. Photographs will be taken to record any clinically significant findings.
- g Brain MRI should confirm presence of BM.

h

CCI

RECIST will also be applied for the evaluation of thorax/abdomen CT images (see Section 5.1 and Section 8.5.4).

i The PI will perform Allen's test at screening and anaesthesiologist will repeat the Allen's test on PET examination day to make sure there is normal flow in the wrist between radial and ulnar arteries.

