j Required at baseline. Repeated during the imaging phase only if clinically indicated at any time point or subsequently at follow-up 30 (± 7) days after last administration of study medication (for example to follow up on a cardiac AE).

k Patient must weigh at least 40.0 kg and no more than 100.0 kg (see Section 3.1).

l Blood and urine samples will be collected for routine laboratory testing (haematology, clinical chemistry), and urine analysis (see Section 5.4).

m Serum pregnancy test at screening and follow-up. FSH and LH to be tested at screening. All other visits, urine pregnancy test.

n Current medications will be reviewed and recorded.

o PK sampling: at pre-administration, 2, 4 and 7.5 hour(s) (can be modified if necessary). During PET examinations, PK sampling schedule maybe limited to the PET examination time (see Section 5.3.2.2).

p CSF samples will be collected at pre-administration prior to start of treatment and at the PET3 examination day.

q A re-biopsy from tissue may be collected as part of clinical routine upon disease progression during continued access treatment. A blood sample (2 x 10 mL) will be collected at screening only for additional option for central confirmation of EGFR status if tissue confirmation is not possible.

r An arterial line will be inserted on the day the patient arrives for the administration of the IP and PET examination. The arterial line will be placed in the opposite arm than the 1 being used to administer the single IV microdose of [¹¹C]osimertinib bolus injection. A venous access line will also be inserted to collect blood samples. The arterial line will be removed at the conclusion of the PET examinations, after the last sample has been collected. The placement of the arterial line, venous access line, administration of the IV microdose [¹¹C]osimertinib bolus injection, PET examinations (see Section 5.3.2.2), and removal of the arterial line (and venous access line) will take place on the same day. Standard institutional procedures will be followed for arterial line removal. In case of failure with arterial sampling during the PET examination, because of spasm or blood clots, the PET examination will continue and venous samples will be taken according to the planned schedule of arterial samples.

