4.3 Continued access phase (CAP)

During the CAP osimertinib can be taken with or without food. Following completion of the imaging phase, patients may continue to take osimertinib as a single agent, if they and the Investigator deem it appropriate, until such time as the Investigator believes they are no longer deriving clinical benefit or they stop taking osimertinib for any other reason. Patients will be seen as per their normal routine clinical schedule. No clinical data will be collected during this phase other than sudden death of unknown reason, SAEs that may be related to osimertinib, outcomes of pregnancy and IP dispensing/accountability.

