4.4 Follow-up period

Descriptions of the procedures for this period are included in the Study Plan with exceptions of the following specific requirements for the follow-up period:

Those patients who do not proceed into CAP will return to the clinic for follow-up assessments 30 days (± 7 days) after their last administration in the imaging phase; follow-up assessments are detailed in Table 1.

If the patient's last administration of osimertinib is in the CAP (ie, after the imaging phase), the patient should be contacted 30 days after their last administration of osimertinib to follow up on any existing SAEs and monitor for new SAEs that may be related to IP.

A post-study assessment will be performed 7 working days after the last [¹¹C]osimertinib has been infused and the PET examination is completed. In the event of a holiday or weather delay the follow-up call may be postponed 1 to 2 working days. If the patient can not be contacted within 14 days as scheduled, the Investigator designee/centre staff must try again.

The patient will be asked about any symptoms or ill-effects since the time of the procedure. The patient will also be reminded to:

- Contact the Investigator or designee at the PET centre, if within the follow-up period following participation in the study, they feel ill effects related to the study.

The post study follow-up call and outcome will be recorded in the patient's medical record.

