7.8 Post study access to study treatment

On completion of the imaging phase (ie, at the PET3 examination), patients may continue to take osimertinib tablets (80 mg once daily) as a single agent in continued access if they and the Investigator agree that this is appropriate. This will continue until the Investigator believes they are no longer deriving clinical benefit, or they stop taking osimertinib for any other reason. No clinical data will be collected during this phase other than sudden death of unknown reason, SAEs that may or may not be related to osimertinib, outcomes of pregnancy and IP dispensing/accountability.

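### The documents contradict each other on whether non-serious adverse events after PET3 are collected for patients who enter continued access

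*Protocol*

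**What the plan says.** Protocol 1.4 sets the phase boundary: "On completion of the imaging phase (ie, at the PET3 examination), patients may continue to take osimertinib tablets". Section 7.8 repeats it. Section 4.3 then limits what is recorded: "No clinical data will be collected during this phase other than sudden death of unknown reason, SAEs that may be related to osimertinib", followed only by pregnancy outcomes and drug accountability. Sections 1.4 and 7.8 carry the same list but admit SAEs whether or not related.

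Several procedures fall on or near that boundary. Footnote p of Table 1 places the second lumbar puncture there: "CSF samples will be collected at pre-administration prior to start of treatment and at the PET3 examination day". The third tracer injection is the same day, with an arterial line unless it is omitted (5.3.2.2), and the patient is discharged once the scan ends (7.2). The second CT and gadolinium MRI need not be on that day: "the CT-2, MRI-2 can be conducted within a window of 7 days" (footnote e).

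The 30-day clinic visit is for patients who do not enter the CAP or who stop treatment in the imaging phase. Section 4.4 also plans a contact 7 working days after the last tracer injection, asking about symptoms since the procedure. On where it is documented: "The post study follow-up call and outcome will be recorded in the" patient's medical record.

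**The concern.** The safety objective covers the tracer injections as well as oral osimertinib. Section 1.3.1 names pain, haematoma, arterial occlusion, local infection and contrast allergy as procedure risks, and says of lumbar puncture: "The procedure may cause temporary headache". Several of these can appear after discharge. The protocol itself allows for a delay, since 3.8 tells patients: "Refrain from hard physical training (such as heavy lifting) for a period of 7 days following arterial catheterisation".

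A site that follows the CAP list would stop recording non-serious events on the day these procedures are done. A site that follows 6.3.1 would record all of them throughout the CAP. It cannot do both. In the first case, an empty record after PET3 could mean either that nothing happened or that nothing was recorded, and the AE tables would not show which.

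**Working it through.** No figure in the plan needs reproducing. The check is a side-by-side reading plus day arithmetic.

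**1. Is a non-serious AE after PET3 recorded for a CAP entrant?**

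| Place | Rule | Answer |
|---|---|---|
| Protocol 1.4, 7.8 | Imaging phase ends at PET3; closed list, SAEs related or not | No |
| Protocol 4.3 (also synopsis, 1.2; SAP 1.2) | Closed list, SAEs possibly related to osimertinib | No |
| Protocol 6.3.1, Table 1 footnote v | All AEs from consent to 30 working days after the product is stopped | Yes, throughout the CAP |
| Table 1 AE review at Visit 7, footnote w | Post-study assessment within 30 working days of the last tracer and PET | Yes, no CAP exception |
| Protocol 6.3.5 | AEs volunteered, or elicited by centre staff, go into the pCRF | Yes |
| Protocol 4.4 | Contact at 7 working days asks about symptoms | Asked; only the medical record is named |
| SAP 3.3 | Treatment-emergent AEs up to 30 days after last study treatment, or until other cancer therapy starts | Presumes yes |

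Sections 6.8.1 and 6.8.2 lean towards the closed list: detailed skin-reaction recording does not apply in continued access, and diarrhoea grade changes are captured during the imaging phase.

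**2. Which procedures are affected, per CAP entrant?** The third of 3 tracer injections; the second of 2 lumbar punctures; the PET3 arterial line, if used; and the second of 2 study MRIs, if done after PET3. Table 1 shows an AE review at Visit 5 (PET3) but none in the MRI2 column (Visit 6).

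**3. Dates.** Section 7.2 puts PET3 on Day 29 ± 3, which is Days 26 to 32. The imaging phase is given as about 32 days, so little or none of it remains after PET3.
- MRI-2 up to 7 days after PET3: Day 29 + 7 = Day 36, or Day 32 + 7 = Day 39.
- Contact at 7 working days: Monday to Wednesday scans give 7 + 2 = 9 calendar days (one weekend); Thursday and Friday scans give 7 + 4 = 11 (two weekends). For PET3 on Day 29 that is Day 38 or Day 40.
- Since 9 > 7, the contact always falls after the latest post-PET3 MRI-2 date. It can therefore cover every procedure in step 2.
- Footnote w: 30 working days is 6 working weeks, 6 × 7 = 42 calendar days.

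**4. Follow-up by group.** Patients outside the CAP are seen 30 ± 7 days after their last imaging-phase dose. CAP entrants have no such visit. SAP 3.3 applies one treatment-emergent window to everyone, and SAP 4.3.3 summarises across all patients.

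**The case against.** The strongest reply is that the plan already collects these events. Section 6.3.1, footnotes v and w and the Visit 7 AE review contain no CAP exception. Section 6.3.5 sends to the pCRF any AE reported in answer to centre staff, and noting the 4.4 call in the medical record does not rule out a pCRF entry. Footnote x asks patients to report ill effects within 30 days. Visit 5 has its own AE review, all SAEs are reportable under 6.4 even when procedure-related, and the PET3 arterial line may be dropped.

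This stands to a large extent. A reader might infer from 1.4 and 4.3 that after-effects of the PET3-day procedures are simply not collected for CAP patients. The documents do not support that, because these other sections point the other way. They do not settle the matter either: 6.3.1 read literally requires all AEs throughout the CAP, which the closed list denies.

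Whether MRI-2 falls inside the CAP is also open to argument. Table 1 is headed as the imaging-phase plan and includes MRI2 as Visit 6, whereas 1.4 and 7.8 end the phase at PET3. The 7-day allowance does not say that MRI-2 must come after PET3.

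A reader might also infer that length of follow-up depends on how well the patient did. That is not established: patients who leave the imaging phase early, including for toxicity, may enter the CAP (3.3, 6.8). There is no comparison group, and the analysis is descriptive.

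**Conclusion.** The point holds as a contradiction between sections, not as a demonstrated absence of collection. If sites work to the closed list, non-serious after-effects arising after discharge from PET3 may be missing from the database for CAP entrants, while patients outside the CAP have about 30 days of AE follow-up under the same treatment-emergent definition.

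The size is best given per patient, as in step 2. One could go further: with 12 patients all completing (12 × 3 = 36 injections, 12 × 2 = 24 lumbar punctures) and 6 to 12 entering the CAP, the affected share would be 6/36 to 12/36 (17% to 33%) of injections and 6/24 to 12/24 (25% to 50%) of lumbar punctures. These figures are illustrative only. CAP entry is assumed, the protocol plans for at least 8 of about 12 patients to complete all assessments, and the figures presume that every site follows the closed list. If all 12 entered the CAP, the mix of follow-up lengths would disappear.

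Figure 1 was not available to check.

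**What to change.** Reconcile Protocol 1.4, 4.3, 4.4, 6.3.1 and 7.8, Table 1 footnotes v and w, and SAP 3.3, as follows:

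- For patients entering the CAP, collect all AEs in the pCRF until the later of MRI-2/CT-2 and the planned post-PET3 contact. CAP-limited collection starts only after that.
- Give the contact a single timing. Seven working days (4.4) is enough to fall after MRI-2. Record it as an AE review in the pCRF as well as in the medical record.
- In SAP 3.3, use the same close-out point for non-serious treatment-emergent AEs in CAP entrants. Their follow-up would still be shorter than in other patients (about 9 to 11 days after PET3, against about 30 days after the last dose), so a footnote to the AE tables should say so.

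The cost is protocol and SAP wording, one pCRF AE-review page, and a few more non-serious events to enter. No visit or procedure is added.
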